4.2.3 Exploratory Endpoints

Ancillary endpoints include: (1) mean systolic BP at 3 months; (2) change in frailty status; (3) attendance at traditional CR; (4) change in depressive symptoms (PHQ-8); (5) barriers to and facilitators of participation from qualitative interviews (subsample of participants).

Ancillary endpoints (*systolic BP, change in frailty status, traditional CR attendance, change in depressive symptoms*) will be measured at the baseline visit, at-home (for intervention group), and at 3-month follow-up visit. Home BP in the intervention arm will be measured with a digital blood pressure cuff provided to participants, which synchronizes with our mHealth-CR software. Frailty will be assessed using the Fried criteria (unintentional weight loss, weakness, exhaustion, slow gait, low physical activity);⁸² we will analyze the number of participants in each group who transition from “frail” to “not frail” between baseline and 3 months. For attendance at traditional CR, we will measure (for each participant) whether traditional CR attended (yes/no), date of first traditional CR visit, number of days from hospital discharge to first traditional CR visit, and total number of traditional CR sessions attended.

The System Usability Scale (SUS) will be used to measure the usability of technology and software in intervention arm participants at the 3-month follow up visit. The SUS is a 10-item questionnaire with five response options ranging from “Strongly Agree” to “Strongly Disagree”. This questionnaire will be administered by the Research Coordinator during the 3-month follow-up visit and open ended feedback will be solicited from the intervention arm subjects

5 Study Enrollment and Withdrawal

5.1 Inclusion Criteria

In order to be eligible to participate in this study, an individual must meet all of the following criteria:

1. Age ≥ 65 .
2. Currently hospitalized for AMI, PCI, or CABG **or**
Hospitalized for AMI, PCI or CABG within prior 4 weeks.
3. Capable of self-consent.
4. Understand and are able to perform study procedures (i.e. 6-minute walk test, use mHealth in English or Spanish).

Given logistical considerations, we expect that most participants with AMI and/or PCI will be recruited from the inpatient setting, with the baseline assessment taking place before discharge. However, given recent trends in AMI and PCI care (shorter hospital stays, including same-day discharge after PCI), we may not be able to capture all eligible participants at the time of hospitalization. In this case, the baseline study visit will take place at the first ambulatory cardiology visit (provided this occurs within 4 weeks of hospitalization). Since patients undergoing CABG have exposure to much greater physiologic stress as they recover from surgery, our expectation is that they will not be enrolled in the hospital (given inability to participate in mHealth-CR immediately after discharge), but instead will be enrolled at the first ambulatory visit (provided within 4 weeks of discharge). For patients with AMI or PCI, they can be enrolled either in the hospital or the first ambulatory visit (provided within 4 weeks of discharge).

5.2 Exclusion Criteria

An individual who meets any of the following criteria will be excluded from participation in this study:

1. Non-ambulatory.
2. Moderate or severe cognitive impairment.

CONFIDENTIAL

This material is the property of the NYU School of Medicine and Langone Medical Center. Do not disclose or use except as authorized in writing by the study sponsor

3. Unable/unwilling to consent.
4. PCI-related groin hematoma that precludes brisk walking.
5. Incarcerated.
6. Unable to use mHealth software in English or Spanish.
7. Severe osteoarthritis, or joint replacement within last 3 months.

Parkinson's disease or other progressive movement disorder.

8. Regular use of walker for ambulation.
9. Projected life expectancy <3 months.
10. Clinical judgment concerning other safety or nonadherence issues.
11. Participants admitted from long-term care facility.
12. Currently listed for heart transplant.
13. Left ventricular assist device recipient.
14. Completion of ambulatory cardiac rehabilitation program within prior 3 months.

5.3 Vulnerable Subjects

The target study population (adults ≥ 65 years) for this research study is unlikely to include women who are of childbearing potential, pregnant or breastfeeding. Participants who are incarcerated are not eligible to participate in this research study. Participants who become incarcerated after randomization will be discontinued from study participation and will be referred to his/ her medical provider for appropriate follow-up treatment. Exclusion of prisoners or incarcerated individuals is due to their inability to use mobile devices and limited internet access during their incarceration.

The target study population may include eligible participants with mild cognitive impairment, since this condition naturally occurs in a significant subset of the older adult population. However, we will exclude participants with overt dementia (cognitive impairment with impaired daily function) if this is mentioned as a diagnosis in the electronic medical record. This is because patients with dementia are unlikely to be able to complete the study protocol.

Impaired decision-making capacity with mild cognitive impairment is very rare.¹¹⁹ If there is any question by the RC regarding impaired decision-making capacity (e.g. due to mild cognitive impairment, delirium, or psychiatric illness), then the UBACC will be administered by a member of the clinical team.

In the event of a new medical illness that has the potential to affect a participant's capacity (e.g. stroke), the UBACC will be re-administered by a member of the clinical team. If at this time the participant no longer has the capacity to consent, the RC or study team member will notify the PI and the participant will be discontinued from the study. Given the relatively short duration of the study, we anticipate that loss of capacity due to many chronic medical illnesses is unlikely.

5.4 Strategies for Recruitment and Retention

Recruitment. Inclusion and exclusion criteria will be determined through screening of the EHR.

The research coordinator will screen the list of patients and send potentially eligible patients to the Principal Investigator for review. At the NYU site, [name], a clinically trained cardiologist, will be responsible for reviewing the list of eligible patients and whether inclusion/exclusion criteria are met. For those deemed eligible, the research team will send an email to the attending physician (usually a cardiologist) notifying that the study team will approach the patient for participation in the research study. [name] and [name] will be responsible at the NYU-Winthrop location for reviewing and confirming eligible patients identified by the NYU-Winthrop coordinator, while [name] will be responsible at the UMMHC site for reviewing and confirming eligible patients identified by the UMMHC research coordinator(s). [name] will be responsible at the Yale site for reviewing and confirming eligible patients identified by the Yale research coordinator(s).

CONFIDENTIAL

This material is the property of the NYU School of Medicine and Langone Medical Center. Do not disclose or use except as authorized in writing by the study sponsor

For eligible patients identified at Bellevue Hospital, the Research Coordinator will send a letter introducing the trial as well as the most current IRB-approved version of the informed consent form. Eligible patients will be called for approach after the letters are sent in order to allow patients to reference the informed consent form during the phone approach. This method will account for high rates of patients at Bellevue Hospital who do not or cannot use email for receipt of informed consent after a phone approach.

Enrollment. For participants currently hospitalized for AMI, PCI, or CABG at the time of screening, participants will be approached in-person by the study team for potential enrollment in the study during a period of clinical stability in the inpatient setting (usually this is close to the time of hospital discharge). Participants who have been discharged from the hospital but are eligible due to recently diagnosed AMI, PCI, or CABG (within 4 weeks of the screening date) will receive a message through the EPIC electronic health record, introducing the participant to the study, and will have the option to “opt out” of being approached by replying to the message. If they do not opt out, they will be approached by the research coordinator for potential enrollment at the time of the next outpatient cardiology visit, provided this occurs within 4 weeks of AMI, PCI, or CABG. In the circumstance that it is not possible for the research coordinator to approach an eligible subject in-person in an inpatient setting, or within 4 weeks of discharge during an outpatient appointment, the research coordinator will call the eligible subject at the preferred phone number in their chart to introduce the study. Eligible patients will have the option of scheduling a research visit to undergo the informed consent process and to complete the baseline visit. For outpatients enrolled in the study, the baseline visit will take place in close proximity to dedicated ambulatory space at NYU Main Campus (Cardiology Faculty Group Practice), NYU Winthrop Campus (Winthrop Cardiology Associates), UMMHC (Ambulatory Care Center), or Yale-New Haven Health (Yale Cardiovascular Medicine, Outpatient Practice).

Participants will be explicitly informed that participation in the present study is voluntary, and will not affect their normal standard of care should they choose not to participate. Participants will be informed that the Principal Investigator will be available by phone or in person for any additional questions participants may have about their involvement. Comprehension of the key elements of the study procedures and risks will be tested with verbal questions of the consent form content. Participants will also be notified of all study-related activities, period of involvement, and contact information of all study personnel. Participants will also be asked to opt-in for future contact by study personnel for additional study-related activities. If the patient is willing to participate, they will sign and date the signature page of the IRB-approved informed consent form. A copy of the signed consent form will be given to the participant and the original will be placed in the research record.

Target enrollment is 400 participants between the NYU, Bellevue, UMass and Yale sites. Male and female participants of all racial backgrounds and ethnicities will be enrolled, without exclusion. We propose a recruitment target for women of at least 40% of the target enrollment participants. We aim to enroll at least 19% nonwhite patients, with at least 12% being black patients, and at least 12% patients of Hispanic ethnicity. If we find that we are not meeting targets for nonwhite and Hispanic enrollment early in our recruitment efforts, we aim to take corrective action including potential addition of other sites to increase diversity, such as Bellevue Hospital.

Retention. At the time of participant enrollment, the research coordinator will complete a participant contact sheet, which will include the participant's name, address, phone number and preferred time for study-related phone calls. The participants will also be asked to provide the contact information (phone numbers) for at least 2 friends or relatives who are aware of the participant's involvement in the study as additional contact person. These individuals will only be contacted in the event that the study participant is unresponsive to communication attempts or if the participant missed a scheduled study visit. Regular phone calls and reminders will be made with participants to maintain retention in the study.

COVID-19 Pandemic: Transportation. In the scenario that study participants encounter difficulties with transportation that would prevent them from attending the baseline and/or follow-up visits (such as inability to schedule their research visit on the same day as a standard of care visit and/or reasons relating to COVID-19 fears) all study participants will be offered free car service until the mask mandate is discontinued by New York State.

5.4.1 Use of Epic Information for Recruitment Purposes

CONFIDENTIAL

This material is the property of the NYU School of Medicine and Langone Medical Center. Do not disclose or use except as authorized in writing by the study sponsor

Inclusion and exclusion criteria will be determined through screening of the EHR primarily by the study research coordinator. A daily report from Epic will be generated based on (1) diagnostic data (classifying patients as having AMI, or undergoing elective coronary revascularization) entered for patients admitted to the hospital from the time of last update (generally last 24 hours during the week except Monday, which captures last 72 hours inclusive of Friday and weekend admissions); and (2) outpatient cardiology appointments scheduled for patients diagnosed with either AMI or who recently underwent elective coronary revascularization (PCI or CABG) within the past 4 weeks. The daily report will be sent to the study research coordinator, who will screen for patients within inclusion criteria and send the list of potentially eligible patients to the Principal Investigator via email for review. Any recruitment information sent by email will utilize Send Safe email.

MyChart Recruitment. If the recruitment sites' electronic health record system supports this feature, participants who have been discharged from the hospital but are eligible due to recently diagnosed AMI, PCI, or CABG (within 4 weeks of the screening date) will receive a MyChart message through the EPIC electronic health record introducing the participant to the study. Participants will have the option to "opt out" of being approached by replying to the message. If they do not opt out or do not have a MyChart account, they will be approached by the research coordinator for potential enrollment at the time of the next outpatient cardiology visit, provided this occurs within 4 weeks of AMI, PCI, or CABG. DataCore will request a daily report of all participants' responses to the MyChart message and send to the research coordinator, who will screen patients within inclusion criteria for potential subject eligibility. Participants who are potentially eligible will be sent to the Principal Investigator via email for review. Any recruitment information sent by email will utilize Send Safe email.

Once contact is made, approved recruitment language will be used to communicate the reason they are being contacted and subjects will be asked if they are interested in participating in this specific study. Should the potential subjects agree, the study team will provide the subjects with information regarding the next steps for participation.

If a subject requests information regarding opting out of further recruitment for all research, subjects will be directed to contact study coordinator or have subjects contact [contact] or [name].

Study members who will have access to the EPIC search results include the Principal Investigator and research coordinator(s). EPIC search results will include the participants' name, date of birth, age, medical record number, medical diagnoses (ICD-9 or ICD-10), lab values, diagnostic test and results (e.g. EKG, echocardiogram), procedural notes and results (e.g. PCI or CABG), and all physician inpatient and outpatient notes in order to determine subject eligibility.

Once eligible subjects have been identified and confirmed by the Principle Investigator, the study team will notify the treating physician (TP) that they have patients eligible to participate in the study via email. If there are no concerns notified by the TP, the research coordinator will approach participant in the inpatient (or outpatient) setting for potential enrollment in the study.

To ensure equitability, the research coordinator will maintain screening logs to characterize the sociodemographics of the patient population and to identify reasons for exclusion. Screening forms will include inclusion/exclusion criteria and basic demographic information (e.g. race, ethnicity, sex).

5.5 Duration of Study Participation

Participants will be asked to participate in the study for 3 months.

5.6 Total Number of Participants and Sites

Recruitment will end when approximately 400 participants are enrolled. Given an estimated 20% drop out rate, the study will enroll approximately 400 participants in order to produce 320 evaluable participants.

CONFIDENTIAL

This material is the property of the NYU School of Medicine and Langone Medical Center. Do not disclose or use except as authorized in writing by the study sponsor

5.7 Participant Withdrawal or Termination

5.7.1 Reasons for Withdrawal or Termination

Participants are free to withdraw from participation in the study at any time upon request. An investigator may terminate participation in the study if:

- Any clinical adverse event (AE), laboratory abnormality, or other medical condition or situation occurs such that continued participation in the study would not be in the best interest of the participant
- The participant meets an exclusion criterion not caused by study procedures (either newly developed or not previously recognized) that precludes further study participation.

5.7.2 Handling of Participant Withdrawals or Termination

Participants wishing to withdraw or that are terminated from the study will be asked if they may continue to be monitored for safety endpoints to capture AEs, SAEs, and unanticipated problems. Survival data on all participants who are lost to follow-up will be kept in the REDCap database (Research Electronic Data Capture), a secure, web-based Electronic Data Capture (EDC) system. Participants who withdraw or are terminated will not return for the 3-month ambulatory assessment.

Participants will be contacted by the study team personnel via phone call at least three times and/or contact with next-of-kin, if possible, before being considered as lost to follow-up. A certified letter will be sent by the study personnel to the participants as final proof of contact.

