4.2 Study Endpoints

4.2.1 Primary Study Endpoints

Primary Efficacy Endpoint. The primary endpoint of this study is the change in the 6MWD between the baseline visit and 3-month follow-up visit. Change in 6MWD, reflective of functional capacity, is measured by the 6-minute walk test (6MWT). The 6MWT will be performed during baseline hospitalization and at the 3-month follow-up visit by a blinded research nurse or exercise therapist.

Primary Engagement Endpoint. Our main measure of engagement is weekly percent completion of the mHealth-CR program. Completion of mHealth-CR analyzed at weekly intervals will allow us to determine distinct engagement trajectories over the 3-month study period. Weekly engagement will be measured as the fraction of the following 11 elements completed each week: (1–7) daily entry of exercise data and RPE; (8) completed weekly phone call with exercise therapist; (9) at least one electronic communication with exercise therapist; (10) watching educational video (which will vary by week); and (11) at least one home BP measurement. Engagement will be assessed as a pseudo-continuous outcome, as the score can range from 0% (0 activities

CONFIDENTIAL

This material is the property of the NYU School of Medicine and Langone Medical Center. Do not disclose or use except as authorized in writing by the study sponsor

completed) to 100% (all 11 activities completed). We will also explore determination of a threshold for minimally sufficient engagement that is associated with improved outcomes.

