7.2.5 Withdrawal/Early Termination Visit

Participants choosing to withdraw or terminate early from the study will not be required to attend the final study visit. Since they are provided with study-related equipment (tablet computer, or if applicable, FitBit and blood pressure cuff), they will be sent a prepaid box to return this equipment to the study team.

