10.3 Analysis Datasets

All randomized participants will be analyzed according to the treatment group to which they were randomized, regardless of subsequent crossover. The intent-to-treat (ITT) population will include all subjects who receive a randomized treatment assignment, except for those with a documented violation of trial eligibility criteria.

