10.4.2 Analysis of the Primary Efficacy Endpoint(s)

6MWD

We will assess the difference in 6MWD by calculating difference scores for each participant and comparing the intervention and usual care groups with an independent group t-tests allowing for unequal variances. We will also regress 3-month 6MWD on a binary indicator of treatment group, with adjustment for baseline 6MWD and the stratification factor (enrollment site). While randomization should obviate the need for additional adjustment, we will explore whether adjustment for participant-level characteristics (e.g., demographic factors or referral to ambulatory CR) is necessary, using the change-in-estimate criterion. We realize that engagement with the mHealth-CR program may also affect attendance and engagement with structured ambulatory CR programs. We intend to explore this as a mediator of the effect of assignment to the intervention arm. We will use structural equation models to estimate the direct and indirect effects of mHealth, where the direct effect is that of mHealth-CR on the 6MWD, and the indirect effect is mediated through attendance at structured ambulatory CR.

Engagement

We hypothesize that (1) among participants offered mHealth-CR, there will be distinct trajectories of engagement (e.g., sustained engagement, disengagement, reengagement, deteriorating engagement); and (2) there will be significant differences in participant characteristics among these groups. While our aim is largely exploratory (given the paucity of data on mHealth-CR engagement), we will test whether the following characteristics are significant: age (≥ 80 years), sex, race/ethnicity, comorbidity burden (≥ 2 chronic medical conditions), frailty, social support (based on living alone), cognitive impairment (based on Mini-Cog), and depressive symptoms (based on PHQ-8). We selected these factors based on literature related to engagement in other technologies. We will conduct latent class analysis to identify profiles of engagement and explore whether these factors indicate membership in a class; these models use maximum likelihood estimation,

CONFIDENTIAL

This material is the property of the NYU School of Medicine and Langone Medical Center. Do not disclose or use except as authorized in writing by the study sponsor

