10.4.4 Safety Analyses

The safety endpoint will be assessed at the 3-month ambulatory visit and includes:

- (1) fall-related injury (operationalized as any fall requiring acute medical care)
- (2) hospitalization for acute coronary syndrome
- (3) hospitalization for unstable arrhythmia

Separately, among intervention participants, study staff will monitor potential exercise-related adverse events on an ongoing basis and report any related AEs to the Principal Investigator. Points of contact will include weekly phone calls with the exercise therapist as well as electronic communication via the mHealth app which is checked daily.

In order to reduce the likelihood of these events, participants will complete the baseline 6MWT in-hospital; if any adverse event occurs during 6MWT (drop in SBP ≥ 15 mmHg, chest pain, ventricular arrhythmia),

CONFIDENTIAL

This material is the property of the NYU School of Medicine and Langone Medical Center. Do not disclose or use except as authorized in writing by the study sponsor

participants will be removed (not randomized). Other exclusion criteria (severe osteoarthritis, recent joint replacement, moderate or severe cognitive impairment) are also intended to minimize risk.

All adverse events will be reported directly to the Principal Investigator and to the DSMB, as outlined in Section 8, Assessment of Safety. Each adverse event will be counted only once for a given participant. Events will be described by start date, stop date, severity, relationship, outcome, and duration. If it is determined that the adverse event precludes further participation in the study among patients in the intervention arm, the study intervention will be discontinued, but participant data will be analyzed using the intention-to-treat principle.

For analysis of the safety endpoint between intervention and control arms, a two-sided significance test with two-sided confidence intervals will be performed (as with the efficacy endpoints).

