10.6 Measures to Minimize Bias

10.6.1 Enrollment/Randomization/Masking Procedures

Randomization. After providing informed consent and completing the baseline assessment, enrolled participants will be randomized by REDCap in a 3:1 ratio to either intervention (mHealth-CR) or control (usual care). The rationale for 3:1 randomization is to efficiently address both the primary comparison of mHealth-CR and usual care with respect to the 6MWD and to allow an adequate sample size to estimate engagement trajectories. The proposed 3:1 randomization enables a 50% increase in the sample size, while also providing excellent power for the primary hypothesis test. Randomization will be stratified by hospital (NYU-main campus, NYU Winthrop, Bellevue, UMMHC, Yale New Haven) to ensure balance across treatment arms given between-hospital population differences. The randomization code will be created by an independent biostatistician, and given to a DataCore staff member, with a backup copy retained by the independent biostatistician.

Missing data. In general, all available data will be included in data listings and tabulations. Population denominators will be displayed in column headers. Individual denominators will be displayed for each summary such that the amount of missing values will be evident. Patients who withdraw from the study or are lost to follow-up will still be included in the denominators for any proportions where data are available.

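### The plan ends 6MWD collection for anyone who withdraws or is terminated, and specifies neither how missing 6MWD and deaths are handled nor a sensitivity analysis

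*Combined protocol and SAP*

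**What the plan says.** **Collection.** The primary endpoint is change in 6MWD from baseline to 3 months. Section 4.2.1 gives two measurement times: "The 6MWT will be performed during baseline hospitalization and at the 3-month follow-up visit". Table 1 shows no other 6-minute walk test (6MWT).

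**Leaving the study.** Section 5.7.2 states: "Participants who withdraw or are terminated will not return for the 3-month ambulatory assessment". These participants are asked only whether safety monitoring may continue. Section 7.2.5 is weaker: "Participants choosing to withdraw or terminate early from the study will not be required to attend the final study visit". Leaving need not be the participant's choice. Section 5.7.1 begins "An investigator may terminate participation in the study if" and goes on to list adverse events, other medical conditions and exclusion criteria met later. Section 10.4.4 covers an adverse event that ends participation in the intervention arm: "the study intervention will be discontinued, but participant data will be analyzed using the intention-to-treat principle". It does not say whether the 3-month visit takes place.

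**Analysis.** Section 10.3 analyses all randomized participants as assigned, "except for those with a documented violation of trial eligibility criteria". Section 10.4.2 specifies an unequal-variance t-test on individual change scores, then adds: "We will also regress 3-month 6MWD on a binary indicator of treatment group, with adjustment for baseline 6MWD", plus enrollment site. The missing-data paragraph in Section 10.6.1 concerns listings, tabulations and denominators. Participants who leave "will still be included in the denominators for any proportions where data are available", but the primary endpoint is a mean, not a proportion. Section 10.5 allows for up to 20% dropout per arm, leaving 320 evaluable of 400.

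**The concern.** A participant without a 3-month 6MWD has no change score and no outcome for the regression. Intention-to-treat then settles which arm people are counted in, but the comparison is between those who completed the visit. Because the investigator can end participation for health reasons, missingness may be related to recovery. In an open-label trial it may also differ between arms.

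If the arms differ in how many values are missing, or in how well the missing participants recovered, the completer difference is biased. The regression removes only the part explained by arm, baseline 6MWD and site. The allowance for dropout protects precision; it does nothing about bias. With no prespecified sensitivity analysis, a reader of a modest result, positive or negative, cannot tell whether it depends on who was missing. A check devised once results are known would carry much less weight.

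**Working it through.** **Inputs (Section 10.5).** 400 randomized 3:1 (300 and 100); up to 20% dropout per arm, leaving 240 and 80; SD of change 60 m; expected gains 60 m and 35 m, so a difference of 25 m; two-sided 0.05.

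**The plan's own figures.** 400 × 0.8 = 320. The SE is 60 × √(1/240 + 1/80) = 7.75 m. The normal approximation gives power of 89.8% at 25 m and 81.1% at 22 m. The unequal-variance t-test gives 89.3% at 25 m. The stated 90% and 80% reproduce, so the sample size is not in question.

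**Significance thresholds.** With 240/80, df = 135.5 and the smallest significant difference is 1.978 × 7.75 = 15.3 m. With 5% missing (285/95), the SE is 7.11 m and the threshold 14.0 m.

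**Bias formula.** Let m be the fraction missing in an arm and g the mean gain of its completers minus the mean gain its missing participants would have had. The bias in the completer difference is m(intervention) × g(intervention) − m(control) × g(control). Equal rates and equal gaps give 0; a gap in the control arm alone reverses the sign.

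**Illustration.** The documents give no g. Assume g = 25 to 40 m in one arm and 0 in the other. Error is the two-sided rejection rate with no true effect.

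| Missing per arm | Evaluable | Bias = m × g | Error |
|---|---|---|---|
| 5% | 285/95 | 1.25 to 2 m | 5.4% to 5.9% |
| 10% | 270/90 | 2.5 to 4 m | 6.3% to 8.5% |
| 20% | 240/80 | 5 to 8 m | 9.8% to 17.6% |

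**Tipping point at the design effect, 20% missing.** Significance is lost when g in the intervention arm reaches (25 − 15.3)/0.2, about 48 m. Missing intervention participants would then have gained 60 − 48 = 12 m, well below the 35 m expected under usual care. If they gained 35 m, the overall difference would be 0.8 × 25 = 20 m, still above 15.3 m.

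**Smaller observed differences.** Suppose missing intervention participants gained only as much as usual care. The overall difference is (1 − m) × D, where D is the completer difference. It falls below the threshold when D < 15.3/0.8 = 19.1 m at 20% missing, or D < 14.0/0.95 = 14.8 m at 5%. So D between 15.3 and 19.1 m (20% missing), or between 14.0 and 14.8 m (5% missing), is significant in completers but not overall.

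The completer SE is held fixed throughout. The SE of the adjusted regression cannot be derived from the documents.

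**The case against.** **Little may be lost through Section 5.7.2.** Ending assessments when consent is withdrawn is normal. Some terminated participants could not take the walk test or would not count: those who lose capacity or are incarcerated (Section 5.3), those who become non-ambulatory (Section 5.2), and documented eligibility violators (Section 10.3). Participants who merely disengage from the programme appear to be expected at the visit, since Section 10.4.11 recruits focus groups across engagement levels after it. All this stands. What remains is the participants terminated by the investigator who would agree and be able to attend.

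**Missing data are watched.** Section 8.8.1 has the DSMB review missed visits and early terminations by treatment group. Section 11 requires missing data to be explained. Section 5.7.3 makes insufficiently complete data a ground for stopping. Section 5.4 has retention measures. Section 10.4.2 explores further covariate adjustment. A reader might infer that the plan ignores missing data; it does not. But none of these provisions tests how far the estimate depends on the unobserved values, and the extra adjustment still uses only participants with a 3-month 6MWD.

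**The sections can be followed together.** A reader might infer a flat contradiction between Sections 5.7.2 and 7.2.5. They differ in strength more than they conflict, and Section 10.4.4 is silent on the visit rather than opposed to either. Still, sites could apply them differently.

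**The vulnerable range lies below the design values.** Differences of 15.3 to 19.1 m are smaller than the 25 m that the plan treats as minimally important and the 22 m at which it claims 80% power. That limits the consequence, but such differences would still be declared significant.

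**Conclusion.** The point holds and should be fixed, at moderate weight. The plan stops collecting the primary outcome from people who withdraw or are terminated, and does not say how missing 6MWD or deaths before 3 months enter the analysis or how dependence on them will be tested.

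The size is conditional. The figures of 1.25 to 2 m at 5% missing and 5 to 8 m at 20% rest on assumed gaps of 25 to 40 m in one arm only, and on missingness from all causes. They do not measure the loss due to Section 5.7.2. A reader might infer that this section accounts for the 20% allowance, or that the trial is biased toward the intervention. The documents support neither: 20% is a planning ceiling for all dropout, the number terminated cannot be derived, and the sign depends on which arm has the larger loss or gap. A 25 m result would be fairly robust; results of about 15 to 19 m with 20% missing might not be.

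**What to change.** 1. Reconcile Sections 5.7.1, 5.7.2, 7.2.5 and 10.4.4 so that stopping the intervention is separate from withdrawing consent to follow-up. Seek the 3-month outcome assessment from every participant who still consents and can attend. Whether the 6MWT itself is performed stays with the investigator and the protocol's existing safety, capacity and incarceration provisions.
2. Tabulate by arm the reasons for missing 6MWD (for example death, loss to follow-up, refusal, termination, inability to walk). Explanations of missing data are already required, so this mainly adds categories and a table.
3. In Section 10.4.2, prespecify a delta-adjusted or tipping-point sensitivity analysis of the baseline- and site-adjusted comparison, varying the two arms separately and stating how deaths are handled. If multiple imputation is used, include variables already collected, such as interim ADL scores, readmission and baseline frailty. Imputing from arm, baseline 6MWD and site alone adds essentially nothing to the regression.

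**Cost.** Protocol wording, a few extra visits by people who have stopped the programme, and modest analysis work. The visit is already scheduled for all participants (Table 1), and transport to it is provided for (Sections 2.3.1 and 15.2).
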